3.3.6. Presentations by Study Visit

When data are collected serially over time, individual data presentations may include by-visit or by-assessment displays. For these presentations, assessments will be presented according to the nominal assessment time as obtained from the eCRF. If the planned visit from the schedule of events is present, it will be used. If it is not present, then the closest assessment to the planned visit will be used. If two assessments have the same distance to the expected study assessment, the earlier value will be used.

All assessments will be presented in the listings.

3.3.7. Definitions and Terminology

Age

The age of a subject is defined as the number of whole years between the subject's birth date and the date of informed consent.

Day 1 (Baseline)

Day 1 is the earliest day that study drug is initiated.

Study Day

Study Day is defined relative to Day 1 as follows: Study Day = Date of event – Date of Day 1 +1*(1 if date of event \geq Date of Day 1, 0 otherwise).

Study Visit

Study Visit is the nominal visit as recorded on the eCRF.

Baseline Value

For purposes of analysis, the baseline value is defined as the last non-missing value obtained prior to initiation of study drug.

Change from Baseline

Change from baseline for a given endpoint is defined as the Study Day X value minus the baseline value.

Percent Change from Baseline

Percent change from baseline for a given endpoint is defined as the Study Day X value minus the baseline value, quantity divided by the baseline value, multiplied by 100.

$$\text{Percent Change from Baseline} = (\text{Study Day X} - \text{Baseline})/\text{Baseline} * 100$$

Days on Study

Days on study is defined as the number of days from the date of study drug initiation to the final study visit (includes in home or in clinic assessments).

Completer

A subject is defined as a completer if he/she completes the Day 26 EEG and Day 27 dosing regardless of completing the Day 33 visit.

Treatment Period

The treatment period is the period during which a subject receives study drug (i.e., first dose through Day 27).

Days on Study Drug

Days on study drug is defined as the number of days in the treatment period. The date of the last dose of study drug as recorded on the End of Study Visit form or from the AICure electronic data transfer.

Total Study Drug Expected (capsules)

The total study drug expected is defined as the total number of capsules expected to be taken as recorded from all sources and reported from the AICure system.

Total Study Drug Received (capsules)

The total study drug received is defined as the total number capsules of taken as recorded from all sources and reported from the AICure system.

Total Study Drug Received (mg)

The total study drug received (mg) amount will be multiplied by 2 for subjects receiving CX-8998 to calculate the amount of study drug received in mg (i.e., each capsule is 2 mg).

Treatment Compliance

Treatment compliance will be calculated for each subject as a percentage using the following formula:

$$\text{total study drug received (capsules)}/\text{total study drug expected(capsules)} * 100$$

Adverse Event

An adverse event is any unfavorable or unintended sign (including an abnormal laboratory finding), symptom, or disease temporally associated with the use of a medical treatment or procedure that may or may not be considered related to the medical treatment or procedure.

Serious Adverse Event

A serious adverse event (SAE) is any adverse event that results in death, is life-threatening, requires in-patient hospitalization or prolongation of existing hospitalization, results in persistent or significant disability/incapacity, is a congenital anomaly/birth defect observed in any offspring of the subject conceived during treatment with the study drug or is an important medical event.

Treatment-emergent Adverse Event

Treatment-emergent adverse events (TEAEs) are all AEs occurring during the treatment period or a pretreatment event that worsens in intensity during the treatment period.

Laboratory Abnormality

Per protocol, a laboratory abnormality is any clinically significant laboratory abnormality suggesting a disease or organ toxicity and which is of a severity requiring active management (i.e., changes of dose, discontinuation of drug, more frequent follow-up, medical treatment or a diagnostic investigation). Laboratory abnormalities may also be recorded as adverse events. While laboratory values are available in the clinical database, assessment of clinical significance is not captured. As such, for analysis purposes, laboratory abnormalities are considered to be any values that are outside of the reported normal range for a given laboratory test.

Treatment-emergent Laboratory Abnormality

Treatment-emergent laboratory abnormalities are all analysis defined laboratory abnormalities occurring in the treatment period that were not within the normal range at baseline.

Concomitant Medications

Concomitant medications are those medications or non-drug therapies taken on or after the initiation of study drug. This definition includes medications started prior to the initiation of study drug that continue to be used concomitantly with study drug.

Orthostatic Blood Pressure

Orthostatic blood pressure is defined as the difference from recumbent to standing in the systolic and diastolic blood pressure measurements.

Seizure Duration

Seizure duration is calculated as the sum of the individual durations of seizures of any type (absence seizures, generalized spike and wave [GSW], focal seizures, focal epileptiform patterns, seizure [other] and electrographic seizure). This is measured in hours.

Absence Seizure Duration

Absence seizure duration is calculated as the sum of the individual durations of absence seizures. This is measured in hours.

Seizure (other) Duration

Seizure (other) duration is calculated as the sum of the individual durations of seizures of any type other than absence seizures (generalized spike and wave [GSW], focal seizures, focal epileptiform patterns, seizure [other] and electrographic seizure). This is measured in hours.

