### **11.5.2 Safety Analyses**

Adverse Events will be mapped to a MedDRA preferred term and system organ classification. Severity will be assessed by investigator. The occurrence of TEAEs will be summarized using MedDRA preferred terms, system organ classifications, and severity. All AEs will be listed for individual subjects; both verbatim and preferred terms will be listed. Separate summaries of treatment-emergent SAEs, AESIs, and AEs leading to discontinuation of study or study drug will be generated.

Descriptive summaries of vital signs and clinical laboratory results will be prepared. The number and percentage of subjects experiencing treatment-emergent laboratory abnormalities and laboratory abnormality shifts from baseline to postbaseline assessments will be summarized.

Concomitant medications will be mapped to a World Health Organization (WHO) Drug Dictionary preferred term and drug classification. The number and percent of subjects taking concomitant medications will be summarized using preferred terms and drug classifications.

Changes from baseline in ECGs during study will be evaluated. Results from the C-SSRS, UM-PDHQ, and physical examinations will be listed.

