5.3. SAFETY AND TOLERABILITY

5.3.1. Safety and Tolerability Endpoints

The primary objective of this study is to assess the safety and tolerability of CX-8998. The following endpoints will be captured and evaluated:

- TEAEs
- changes from baseline in QTcF and other electrocardiogram (ECG) parameters
- changes from baseline in clinical safety laboratory assessments (clinical chemistry, hematology, and urinalysis)
- changes from baseline in vital signs
- number (%) of subjects who did not complete the study due to TEAE
- number (%) of subjects with SAE
- number (%) of subjects with Adverse Events of Special Interest (AESI) from the AE pages of the CRF:
 - Increased seizure frequency
 - New seizure types
 - Status epilepticus
- Columbia Suicide Severity Rating Scale (C-SSRS)
- Epworth Sleepiness Scale (ESS)

- University of Miami Parkinson's Disease Hallucinations Questionnaire (UM-PDHQ)

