5.3.2.2. Clinical Laboratory Assessments

Actual values and changes from baseline in clinical laboratory assessments will be summarized by study visit.

Laboratory values outside the normal range for each parameter will be identified using shift tables. Each subject's hematology and blood chemistry values will be flagged as "low" (below the lower limit of normal/LLN), "normal" (within the normal range), or "high" (above the upper limit of normal/ULN) relative to the normal ranges of the central laboratory. Each subject's urinalysis values will be flagged as "normal" or "abnormal."

Shifts from baseline to high/normal/low status for hematology and blood chemistry parameters will be presented by study visit. Shifts from baseline to normal/abnormal status for urinalysis will be presented by study visit.

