7. CHANGES IN THE PLANNED ANALYSES FROM THE PROTOCOL

Changes to the planned analysis from protocol:

The following endpoints will not be summarized:

- The change in frequency (number of seizures per hour) of absence seizures as defined by a 3-Hz spike and wave lasting for ≥ 3 seconds as determined by hyperventilation (HV)
- The frequency (number of seizures per hour) of absence seizures (based on 6.5-hour video-EEG)
- The time to absence seizures during HV

- The percent of subjects with a shift in the occurrence of absence seizure (e.g., from HV period 1 to HV period 2)
- The percent of subjects with an absence of photic response.
- Change in seizure duration (determined by ambulatory EEG)
- Change in spike-wave run duration (determined by ambulatory EEG)
- Change in spike-wave density (spike-wave %) (determined by ambulatory EEG)
- Proportion of subjects with 30% and 50% reduction in seizure frequency (responder rate) and proportion of seizure-free subjects (determined by ambulatory EEG)
- Seizure-free intervals in minutes (maximum and average determined by ambulatory EEG)
- Change in the Seizure-related Disability Assessment Scale (SERDAS)
- Change in the average weekly seizure frequency for each type of seizure self-reported by subjects in the daily seizure diary
- Changes in the number of seizures recorded with the Epitel device (based on device availability)
- Relationship between the EEG parameters and the PK of CX-8998
- Exposure-response and exposure-safety relationships using plasma concentrations of CX-8998 and its 2 primary metabolites (M01 and M02) in population PK/PD analyses

Should any additional deviations from the analyses specified in the authorized statistical analysis plan arise, such deviations will be documented in the final clinical study report.

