14.3.4.1 Summary of Hematology Assessments

14.3.4.2 Summary of Serum Chemistry Assessments

14.3.4.3 Summary of Coagulation Assessments

14.3.4.4 Summary of Urinalysis Assessments

14.3.4.5 Shift from Baseline of Laboratory Abnormalities

14.3.5.1.1 Summary of Electrocardiogram Parameters

14.3.5.1.2 Summary of Electrocardiogram Outliers

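### The SAP's definition of a treatment-emergent laboratory abnormality is inverted: it requires an out-of-range baseline, so it misses new abnormalities and counts old ones

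*SAP*

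**What the plan says.** SAP 3.3.7 builds the definition in two steps. It first notes that clinical significance is not captured in the database, and so "for analysis purposes, laboratory abnormalities are considered to be any values that are outside of the reported normal range for a given laboratory test". It then defines the treatment-emergent subset as analysis-defined "laboratory abnormalities occurring in the treatment period that were not within the normal range at baseline".

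The same section defines treatment-emergent adverse events as "all AEs occurring during the treatment period or a pretreatment event that worsens in intensity during the treatment period".

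For reporting, protocol 11.5.2 commits to two things in one sentence: "The number and percentage of subjects experiencing treatment-emergent laboratory abnormalities and laboratory abnormality shifts from baseline to postbaseline assessments will be summarized". SAP 5.3.2.2 plans actual values, changes from baseline and shift tables: "Shifts from baseline to high/normal/low status for hematology and blood chemistry parameters will be presented by study visit". Urinalysis is handled there as normal or abnormal only. SAP Section 7 opens its list of dropped analyses with "The following endpoints will not be summarized", and no laboratory summary appears in that list. Among the laboratory tables in SAP Section 10, the only one concerned with abnormalities is "14.3.4.5 Shift from Baseline of Laboratory Abnormalities".

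**The concern.** In ordinary use, treatment-emergent means new since treatment started, or worse than before it. The laboratory definition says nearly the reverse: the subject must already have been out of range, and no worsening is required. It is inconsistent in concept with the adverse event definition in the same section, under which something already present counts only if it worsens.

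Safety is the primary objective, and the protocol promises a count and percentage of subjects with these abnormalities. A programmer who follows the sentence would build an inverted flag, and a second programmer validating against the same sentence would reproduce it. The resulting percentages would disagree with the shift table made from the same data. Nothing in SAP 3.3.5 (incomplete dates), 5.3.2.2, Section 7 or Section 10 restates or corrects the rule.

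**Working it through.** The plan gives no figure to reproduce; the question is which transitions the wording counts.

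**Inputs.** Abnormality means any out-of-range value (SAP 3.3.7). Baseline is the last non-missing value before study drug (SAP 3.3.7). Hematology and chemistry values are flagged low, normal or high, and urinalysis normal or abnormal (SAP 5.3.2.2).

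**Step 1: enumerate the transitions.** Three baseline states by three on-treatment states give 9 cells. Three end in normal and cannot be abnormalities. The other six are:

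| Baseline to on-treatment | SAP rule as written | Normal baseline or opposite-side crossing | SAP rule with *not* deleted |
|---|---|---|---|
| normal to low | no | yes | yes |
| normal to high | no | yes | yes |
| low to high | yes | yes | no |
| high to low | yes | yes | no |
| low to low | yes | no | no |
| high to high | yes | no | no |
| **Cells counted** | **4** | **4** | **2** |

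The rule as written and the second rule agree on 2 cells, the crossings. The written rule misses both normal-to-abnormal cells and adds both same-side cells. It counts same-side values whether they are stable, worse, or better but still out of range. Against the version with *not* deleted, it has no cell in common.

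For urinalysis, the written rule counts only abnormal to abnormal; the second rule counts only normal to abnormal. There is no overlap.

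**Step 2: effect on a count.** For one test, let *B* be the subjects out of range at baseline and still out of range on treatment, *C* those among *B* who cross to the opposite side, and *N* those normal at baseline who become abnormal. Then:

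- count as written = *B*
- count under the second rule = *N* + *C*

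The written count does not depend on *N*, the number of subjects with a new abnormality.

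**Step 3: illustration.** The number 15 is the planned ceiling in SAP 3.1. The values of *B*, *C* and *N* are assumptions: *B* = 3, leaving 15 − 3 = 12 with a normal baseline; *N* = 0, 4 or 12; *C* = 0 or 1.

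| *N* | *C* | As written, *B*/15 | Second rule, (*N* + *C*)/15 |
|---|---|---|---|
| 0 | 0 | 3/15 = 20% | 0/15 = 0% |
| 4 | 0 | 3/15 = 20% | 4/15 = 27% |
| 12 | 0 | 3/15 = 20% | 12/15 = 80% |
| 0 | 1 | 3/15 = 20% | 1/15 = 7% |
| 4 | 1 | 3/15 = 20% | 5/15 = 33% |
| 12 | 1 | 3/15 = 20% | 13/15 = 87% |

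**Step 4: where the definition is used.** The primary laboratory endpoint in SAP 5.3.1 is "changes from baseline in clinical safety laboratory assessments", which does not need it. Neither do the shift tables, the listings or adverse event reporting. The one summary that does need it is the count and percentage in protocol 11.5.2, which is promised, not withdrawn in SAP Section 7 and not scheduled in SAP Section 10.

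**The case against.** The strongest reply is that the definition feeds no listed output. The SAP does not use the term in describing any analysis, and no table in Section 10 is a treatment-emergent count. Laboratory tests have one scheduled draw after dosing starts, on Day 26, so the normal-to-low and normal-to-high cells of Table 14.3.4.5 already show, test by test, the scheduled abnormalities that the definition would miss. Protocol 11.5.2 names the count and the shifts together and does not ask for separate tables. On this view the sentence is a drafting slip with little consequence.

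Much of that is right, and it limits the damage. It does not remove the problem. The shift table does not give a number of subjects across tests, and unscheduled draws may be visible only in the listings. The count therefore remains a protocol commitment that the SAP neither drops nor schedules, and its only definition gives the wrong answer. If Table 14.3.4.5 is meant to satisfy the commitment, the SAP should say so.

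Two further points are fair. Counting opposite-side crossings is a choice the documents do not make; deleting *not* would also cure the inversion, though it would drop the crossings. And the proposed rule leaves out same-side worsening, so it does not mirror the adverse event definition fully. With no severity grade for laboratory values, counting worsening would need a pre-specified threshold that the SAP does not have.

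**Conclusion.** The concern holds. Read as written, SAP 3.3.7 excludes every normal-to-abnormal change and includes abnormalities already present and no worse. It is probably a drafting inversion, but nothing in the documents corrects it.

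The logical result, 2 of 4 counted cells shared with a sensible rule, needs no assumption beyond the choice of comparison rule; with *not* deleted as the comparison, the overlap is zero. The percentages in the illustration do rest on assumed inputs, including that all three baseline-abnormal subjects stay out of range. They show how far a count could go wrong and do not predict this trial's data.

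The consequence is confined to the summary promised in protocol 11.5.2 and any flag derived from the sentence. It should be corrected before the laboratory flags are programmed.

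**What to change.** Replace the sentence in SAP 3.3.7 with wording such as:

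> A treatment-emergent laboratory abnormality is an out-of-range value in the treatment period for a test whose baseline value was in range, or was out of range on the other side (low to high, or high to low).

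For urinalysis this reduces to normal to abnormal. Leave same-side worsening to the change-from-baseline summaries unless a threshold is pre-specified. State how a test with no baseline value is treated, which the present wording leaves open.

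Then either add the count-and-percentage table to SAP Section 10, or record in Section 7 that it is omitted and whether Table 14.3.4.5 stands in for it.

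The cost is a short SAP wording change and one derived flag, plus one table or one line in Section 7. No new data are needed.

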3.4. TIMING OF ANALYSES

The final analysis will be completed after the last subject completes or discontinues the study and the resulting clinical database has been cleaned, quality checked, and locked.

4. ANALYSIS POPULATIONS

The populations defined for analysis will include the intent-to-treat (ITT) population, safety population, and a pharmacokinetic (PK) population.

4.1. INTENT-TO-TREAT (ITT) POPULATION

The ITT population will include all subjects enrolled. This analysis population reflects the full analysis set for this study. The ITT population will be used for analyses of accountability, demographics, and efficacy.

4.2. SAFETY POPULATION

The safety population will include all subjects who are enrolled and receive at least one dose of study drug. The safety population will be the primary population for all analyses of safety data.

4.3. PK POPULATION

The PK population will consist of all subjects in Safety Population who have at least one nonmissing plasma concentration data for CX-8998 and /or its metabolites

5. STATISTICAL METHODS

Descriptive statistical methods will be used to summarize the data from this study. Unless stated otherwise, the term “descriptive statistics” refers to number of subjects (n), mean, median, standard deviation, minimum and maximum for continuous data, and frequencies and percentages for categorical data. Presentations of data will be summarized in an overall manner. All available data for enrolled subjects will be listed in the data listings. Unless otherwise noted, the data will be sorted first by subject number and then by date within each subject number.

The statistical analyses will be conducted with the SAS® System version 9.4 or higher.

5.1. SUBJECT DISPOSITION, DEMOGRAPHIC AND BASELINE CHARACTERISTICS, AND EXTENT OF EXPOSURE

Subject disposition will be presented for all enrolled subjects. The number of subjects enrolled will be presented for each study population and site. The number of subjects who completed the study and discontinued from the study will be provided. The primary reasons for discontinuation from the study at any point also will be presented. Days on study will be summarized.

Demographic data and baseline characteristics including age, gender, race, ethnicity, height, weight will be summarized using descriptive statistics for the ITT population.

Extent of exposure will be summarized for the safety population using the following measures: days on study drug and total study drug received (in mg), as estimated by the number of capsules dispensed and returned. Treatment compliance also will be summarized. The number and percentage of subjects requiring a dose reduction will be summarized.

5.2. CONCOMITANT MEDICATIONS AND NON-DRUG THERAPIES

Concomitant medications and non-drug therapies will be mapped to a World Health Organization (WHO) preferred term and drug classification (Anatomic Therapeutic Chemical Classification level 4): WHODrug March 2018. The number and percent of subjects taking concomitant medications or undergoing non-drug therapies will be summarized using preferred terms and drug classifications and sorted by descending total number of subjects. Determination of concomitant status will be determined according to the rules outlined in Section 3.3.5.

5.3. SAFETY AND TOLERABILITY

5.3.1. Safety and Tolerability Endpoints

The primary objective of this study is to assess the safety and tolerability of CX-8998. The following endpoints will be captured and evaluated:

- TEAEs
- changes from baseline in QTcF and other electrocardiogram (ECG) parameters
- changes from baseline in clinical safety laboratory assessments (clinical chemistry, hematology, and urinalysis)
- changes from baseline in vital signs
- number (%) of subjects who did not complete the study due to TEAE
- number (%) of subjects with SAE
- number (%) of subjects with Adverse Events of Special Interest (AESI) from the AE pages of the CRF:
 - Increased seizure frequency
 - New seizure types
 - Status epilepticus
- Columbia Suicide Severity Rating Scale (C-SSRS)
- Epworth Sleepiness Scale (ESS)

- University of Miami Parkinson's Disease Hallucinations Questionnaire (UM-PDHQ)

5.3.2. Safety Analysis

5.3.2.1. Vital Signs and ECGs

Descriptive statistics will be presented for actual values and for the change from baseline values for systolic and diastolic blood pressure, pulse rate, respiration rate, and weight by study visit. Blood pressure summaries will include recumbent and standing measurements, as well as the change from recumbent to standing (orthostatic changes).

Incidence of vital signs outliers will be presented by visit and time point, where applicable. Outliers for recumbent and standing vital sign parameters will be determined using the criterion in Table 1.

Descriptive statistics will be presented for actual values and for the change from baseline values for the ECG parameters of heart rate (bpm), PR interval (msec), QRS duration (msec), QT interval (msec), QTc interval (msec), and QTcF interval (msec) will be summarized by treatment group and study visit.

The incidence of ECG outliers will also be summarized by visit according to the following criteria:

- $QT > 500$ msec
- $QTcF > 450$ msec for males or $QTcF > 470$ msec for females
- $QTcF$ increases from baseline or pre-dose:
 - ≤ 30 msec
 - > 30 msec to ≤ 60 msec
 - > 60 msec

Table 1. Outliers for recumbent and standing vital sign parameters

Vital Sign	Criteria
Temperature	>38°C and $\geq 1^{\circ}\text{C}$ increase from baseline
Pulse	>120 bpm and >30 bpm increase from baseline <50 bpm and >20 bpm decrease from baseline ≥ 20 bpm increase from baseline ≥ 40 bpm increase from baseline ≥ 20 bpm decrease from baseline ≥ 40 bpm decrease from baseline
Systolic blood pressure	>180 mmHg and with >40 mmHg increase from baseline <90 mmHg and with >30 mmHg decrease from baseline ≥ 20 mmHg increase from baseline ≥ 40 mmHg increase from baseline ≥ 20 mmHg decrease from baseline ≥ 40 mmHg decrease from baseline
Diastolic blood pressure	>105 mmHg and with >30 mmHg increase from baseline <50 mmHg and with >20 mmHg decrease from baseline ≥ 10 mmHg increase from baseline ≥ 20 mmHg increase from baseline ≥ 10 mmHg decrease from baseline ≥ 20 mmHg decrease from baseline

